## **C.4. Sample Size**

This pilot study will use a feasibility-based sample size, determined by the total number of OPD clinicians available at [name] Hospital. We anticipate enrolling approximately 16 participants, representing all nurses, clinical officers, and nursing assistants currently working in the OPD of [name] Hospital. Each participant will complete 12 simulated scenarios, yielding an estimated 192 scenario-level observations. While not powered to detect small effect sizes, this sample is deemed to be sufficient to assess feasibility, refine study procedures, and provide preliminary effect estimates to inform the design and power calculations of a subsequent larger trial.

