### C.9. Outcomes

Primary outcome:

- Guideline-adherent management: Proportion of pre-specified, guideline-consistent critical management actions (diagnostics and treatments) completed per vignette (proportion 0-1). Participant responses recorded at the initial assessment and post-investigation stages will be scored against a gold-standard answer key derived from WHO guidelines (Basic Emergency Care assessment checklists, ETAT performance checklists, Integrated Management of Childhood Illness checklists). Scoring will be performed by two independent assessors, blinded to allocations, mapping free text to binary items (performed correctly vs. not performed/incorrect). Disagreements will be resolved by consensus.

Secondary Outcomes:

- Triage accuracy: Correct assignment to Interagency Integrated Triage Tool (IITT) category (Red/Emergency, Yellow/Urgent, Green/Non-urgent) compared with the case-specific expected category (binary). Scoring will be performed by two independent assessors, blinded to allocations.
- Disposition appropriateness: Appropriateness of the disposition decision (hospitalize, discharge) compared with case-specific expected disposition in the answer key, based on

WHO/Uganda guidelines (binary). Scoring will be performed by two independent assessors, blinded to allocations.

- Diagnostic accuracy: Correctness of working impression (initial stage) and final diagnosis (post-investigation stage), compared with case-specific diagnostic labels in the answer key, based on WHO/Uganda guidelines (binary). Scoring will be performed by two independent assessors, blinded to allocations, mapping free text to binary items (performed correctly vs. not performed/incorrect).
- Guideline-adherent evaluation (process quality): Proportion of critical history and examination items elicited by the participant during the vignette, compared with case-specific list of critical items derived from WHO guidelines (proportion 0-1). Scoring will be performed by two facilitators during each simulation session using the facilitator tick-box logs.
- Time to completion: Duration needed to complete each vignette, measured by facilitators (continuous).
- Usability: Total score on System Usability Scale (SUS), a widely validated 10-item tool for evaluating software systems in healthcare and other fields (continuous).

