### C.11. Statistical Analysis

All analyses will follow the intention-to-treat principle. For vignette-level outcomes, if a participant does not complete an entire scenario, that scenario will be excluded from analysis. Within completed scenarios, missing or blank responses will be treated as incorrect (i.e., non-adherent), on the assumption that an unanswered item reflects lack of knowledge or failure to act. For survey outcomes, only available responses will be analyzed, with no imputation. Descriptive statistics will therefore be based on the number of participants who provided a response to each item. The number of missing scenarios and survey responses will be reported.

The primary analysis will follow a crossover design, with each participant contributing observations under both study conditions (App-assisted vs. control) across distinct but content-equivalent case scenarios:

- Guideline-adherent management: Analyzed as a bounded proportion (0-1) using a generalized linear mixed-effects model with binomial distribution and logit link. The model will include fixed effects for study arm (App vs. control), period (first vs. second session), sequence (allocation order), scenario type (diarrhea, dyspnea, seizure), cadre (clinical officers vs nurses), years of experience (continuous), baseline comfort in using mobile Apps (dichotomous). Random intercepts will be specified for participant to account for repeated measures. Results will be reported as adjusted mean differences with 95% CIs. Inter-rater reliability will be assessed using Cohen's  $\kappa$  for individual items and intraclass correlation coefficients (ICC) for total checklist scores.
- Triage appropriateness, disposition appropriateness, and diagnostic accuracy: Each will be analyzed as binary outcomes (correct vs. incorrect) using mixed-effects logistic regression, with the same fixed and random effects structure as above. Results will be reported as adjusted odds ratios with 95% CIs. Inter-rater agreement will be evaluated using Cohen's  $\kappa$ .

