- Guideline-adherent evaluation (proportion score): Analyzed as a bounded proportion (0-1) using a generalized linear mixed-effects model with binomial distribution and logit link, with the same fixed and random effects as above. Results will be reported as adjusted mean differences with 95% CIs. Inter-rater reliability will be assessed using Cohen's  $\kappa$  for individual items and intraclass correlation coefficients (ICC) for total checklist scores.
- Time to case completion (minutes): Analyzed as a continuous outcome using a linear mixed-effects model. Results will be reported as adjusted mean differences with 95% CIs.

As a sensitivity analysis, a first-exposure parallel analysis will be conducted, in which only the first period for each participant is analyzed. This eliminates potential carryover or learning effects, at the cost of reduced sample size. Findings from the crossover and first-exposure analyses will be compared to assess robustness. Multiplicity across secondary outcomes will be managed by treating the crossover analysis of the primary outcome as the only confirmatory analysis, with all secondary outcomes considered exploratory.

Survey outcomes, including SUS scores and additional Likert-scale items (perceived usefulness, trust, satisfaction, feasibility), will be summarized descriptively and reported as medians with interquartile ranges or proportions, as appropriate.

Qualitative data will be analyzed by two researchers using inductive thematic analysis to identify key themes related to usability and feasibility, and to guide further App refinement.

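### C.11 does not say how item counts enter the binomial model or how correlation within a vignette is handled, so the primary interval could be too wide or too narrow

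*Combined protocol and SAP*

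**What the plan says.** C.9 defines the primary outcome as "Proportion of pre-specified, guideline-consistent critical management actions (diagnostics and treatments) completed per vignette (proportion 0-1"). Two blinded assessors build it by "mapping free text to binary items (performed correctly vs. not performed/incorrect"), so a numerator and a denominator exist for every vignette.

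C.11 specifies the model: "Analyzed as a bounded proportion (0-1) using a generalized linear mixed-effects model with binomial distribution and logit link". On clustering it says: "Random intercepts will be specified for participant to account for repeated measures". The process-quality score is handled the same way: "Analyzed as a bounded proportion (0-1) using a generalized linear mixed-effects model". For neither outcome does C.11 give a number of trials, weights, a dispersion parameter, a robust variance or a vignette-level term. Both effects are to be reported as adjusted mean differences with 95% intervals. C.11 makes the crossover analysis of the primary outcome the sole analysis designated confirmatory.

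The item count for the primary score is not fixed in C.9 or C.11. The assessor sheet in Appendix E, used for all cases, lists six boxes under the management heading: triage, immediate treatments, investigations, diagnosis, disposition, and treatment and follow-up. C.9 limits the primary outcome to diagnostics and treatments, which fits three of those boxes.

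On size, C.4 says: "We anticipate enrolling approximately 16 participants", and "Each participant will complete 12 simulated scenarios, yielding an estimated 192 scenario-level observations".

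**The concern.** A binomial likelihood takes its variance from the number of trials. If a proportion is supplied without that number, each vignette is treated as one yes/no trial with variance p(1-p), although the score averages several items. The stated standard error is then generally too large.

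Supplying the counts removes that error but exposes another. With a participant intercept only, the items of one vignette are taken as independent given the participant. The example case in Appendix E makes this doubtful: the judgement about hydration status underlies the immediate treatment, the decision on tests and the later plan, so one misjudgement can fail several items together. The standard error is then too small.

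The width of the confirmatory interval would therefore rest on a coding choice that the plan leaves open and that could be made after the results are seen. C.4 also intends the estimates to inform the power calculation of a larger trial.

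**Working it through.** **Inputs from the documents.** 16 participants and 12 scenarios each (C.4); six scenarios per arm (C.8); binary items (C.9); participant intercept only (C.11).

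**Assumptions, because the documents give no figure.** Items per vignette m = 3 to 8. Three is the number of treatment and investigation boxes in Appendix E, six is the whole sheet, and eight is borrowed from the process-quality score of the sample case in Appendix C. Adherence is 0.50 against 0.65 in step 2 and about 0.55 in both arms in step 4. Participant SD is 0.5 on the logit scale.

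**1. The plan's own figure.** 16 × 12 = 192, which reproduces. Per arm: 16 × 6 = 96 vignettes.

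**2. What the denominator does, with independent items.** The half-width of the 95% interval for the difference is 1.96 × √[(0.50 × 0.50 + 0.65 × 0.35)/(96m)]. Without counts (m = 1) this is 1.96 × √(0.4775/96) = 0.138. With m = 3, 6 and 8 it is 0.080, 0.056 and 0.049.

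**3. With correlation ρ between items of one vignette.**
- SE without counts / true SE = √[m/(1 + (m − 1)ρ)]. For m = 6 this is 2.45 at ρ = 0, 2.0 at 0.1, 1.55 at 0.3, 1.31 at 0.5 and 1.0 at 1.
- SE with counts / true SE = 1/√[1 + (m − 1)ρ]. For m = 6 this is 1.0 at ρ = 0, 1/1.22 = 0.82 at 0.1 and 1/1.58 = 0.63 at 0.3.

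**4. Simulation.** Two hundred 16 × 12 crossover trials per setting, with no App effect. Each was fitted by maximum likelihood with arm, period, sequence, scenario type and a participant intercept, once as a bare proportion and once as k of m items. Cadre, experience and app comfort were left out; they vary between participants and should hardly affect a within-participant contrast. Ratios are mean model SE divided by the empirical SD of the estimated log-odds ratio. False positives are 100% minus coverage.

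| m | Vignette SD | Bare: SE / SD | Ratio | Counts: SE / SD | Ratio | Counts: false positives |
|---|---|---|---|---|---|---|
| 3 | 0 | 0.294 / 0.168 | 1.75 | 0.173 / 0.175 | 0.99 | 3.5% |
| 3 | 0.7 | 0.293 / 0.184 | 1.59 | 0.173 / 0.192 | 0.90 | 9.5% |
| 3 | 1.2 | 0.293 / 0.191 | 1.53 | 0.172 / 0.198 | 0.87 | 9.5% |
| 6 | 0 | 0.292 / 0.119 | 2.45 | 0.122 / 0.125 | 0.98 | 6% |
| 6 | 0.7 | 0.292 / 0.139 | 2.10 | 0.122 / 0.145 | 0.84 | 11.5% |
| 6 | 1.2 | 0.292 / 0.155 | 1.89 | 0.122 / 0.161 | 0.76 | 15% |
| 8 | 0 | 0.292 / 0.105 | 2.79 | 0.106 / 0.110 | 0.96 | 5% |
| 8 | 0.7 | 0.292 / 0.126 | 2.32 | 0.106 / 0.132 | 0.80 | 14% |
| 8 | 1.2 | 0.292 / 0.148 | 1.96 | 0.105 / 0.155 | 0.68 | 19% |

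The bare fit covered 99.5% to 100% throughout, and its SE stays near 0.29 whatever m is.

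Two further simulations agree:
- 150 trials per setting, vignette SD 0.5 and 1.0, m = 3, 6 or 8: bare ratio 1.51 to 2.26 with no false positives; count ratio 0.70 to 0.96 with about 5% to 19%.
- 100 trials per setting, m = 3 or 6: bare ratio about 1.3 to 2.8; with counts and vignette SD 0.7 to 1.0, ratio about 0.76 to 1.0 with 4% to 16% false positives.

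**5. If the App effect varies between participants.** With SD s on the logit scale, s²/16 is added to the true variance. The bare SE becomes correct when 0.29² = SD² + s²/16. For m = 6, s² = 16 × (0.0841 − 0.0142) = 1.12, so s is about 1.06. The count fit would then be far too narrow: 0.122/0.29 = 0.42.

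**The case against.** The strongest reply is that the concern argues from silence. A proportion with a binomial distribution and logit link is also a usual short description of a k-of-m fit. The score is built from binary items, C.11 itself mentions individual items and total checklist scores, and Appendix C records the process score over a denominator of eight. This stands: the plan never says that counts will be left out.

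A reader might therefore infer too much by concluding that the primary interval will be far too wide. The documents do not support that. Under the count reading the error runs the other way, and the excess under the bare reading shrinks with item correlation or with variation in the App effect.

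A reader might also infer that power is largely lost. The simulations had no App effect and did not measure power. A rough normal approximation shows that the loss depends on the effect. Take m = 6, bare SE 0.29 and true SD 0.145; the estimate must exceed 1.96 × 0.29 = 0.568. From 0.50 adherence, gains of 20, 15 and 10 points are log-odds ratios of 0.847, 0.619 and 0.405. Subtracting 0.568 and dividing by 0.145 gives 1.92, 0.35 and −1.12, that is, power of about 97%, 64% and 13%. C.4 already says that the pilot is not powered for small effects.

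It is also fair that m and the variances are assumed, and that with three items and modest correlation the count fit is nearly right (0.96 at vignette SD 0.5). What does not stand is that this is only missing detail. The random-effects structure is stated, and it leaves no room for correlation within a vignette under either reading. If the bare SE happens to be right, that is coincidence.

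**Conclusion.** The concern holds as a gap with consequences in either direction. C.11 leaves open how the denominator enters and makes no provision for correlation within a vignette, for the confirmatory outcome and for process quality.

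- Fitted without counts: SE roughly 1.3 to 2.8 times the true SE for 3 to 8 items, with the excess shrinking as item correlation rises or if the App effect differs between participants.
- Fitted with counts and the planned participant intercept: about right if items are independent; otherwise SE about 0.7 to 1.0 of the true SE and a false-positive rate of about 5% to 19%, for vignette SD 0.5 to 1.0.

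The directions follow from the model structure. The sizes rest on assumed item counts, adherence and variance components, and on 100 to 200 simulated trials per setting. Pilot status lessens the consequence but does not remove it, because interval estimates are the main quantitative product. The model should be settled before any analysis by arm.

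**What to change.** In C.11, for both proportion outcomes, replace the model sentence with wording to this effect: the response is the number of critical items correct out of the number scored in that vignette, in a binomial-logit mixed model with random intercepts for participant and for participant-by-vignette (or a beta-binomial equivalent). Intervals use a small-sample method or a bootstrap that resamples whole participants. The adjusted mean difference is obtained by marginal standardisation from that model. The participant-level bootstrap also allows for an App effect that differs between participants, which neither random intercept does.

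Supplying counts alone is not enough. The denominator must also be defined: list the scored items and their number for each case, and reconcile the six-box sheet in Appendix E, which includes triage, diagnosis and disposition, with C.9, which admits diagnostics and treatments only.

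The cost is SAP wording, a decision on the scoring sheet, slightly more analysis work and one extra variance term. With few items per vignette that term may be weakly estimated, so the plan should say what is done if it is estimated at zero. No new data are needed, because the binary items are already to be scored. The amended model was not simulated here; the case for it is that it contains the term that the planned model lacks.

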### C.8. Simulation and Scenarios

Each participant will complete 12 facilitated clinical vignette scenarios, with six scenarios per study arm (two diarrhea, two dyspnea, and two seizures). Scenarios will be adapted from WHO training materials for emergency care (e.g., *Basic Emergency Care* course, *Emergency Triage Assessment and Treatment* guidelines) and tailored to reflect common emergency presentations in the OPD of [name] Hospital. Both adult and pediatric cases will be included, varying in severity and presentation to capture the spectrum of conditions typically encountered. Draft cases will undergo expert review and pilot testing with representative clinicians to ensure clarity, realism, and contextual relevance. Cases will be designed in matched pairs to ensure comparable content and difficulty between study periods, with equivalence determined by expert review and pilot testing. Scenarios will be balanced for complexity, number of critical actions, and expected completion time.

Cases will be delivered verbally by a trained facilitator, who will respond only to participant questions to simulate real-world information gathering. Facilitators will log which key history and examination items are elicited using a structured tick-box script.

At two predefined points in each vignette, participants will record their diagnostic and treatment plan:

1. Initial assessment stage – working impression, immediate treatments, and diagnostic tests ordered.
2. Post-investigation stage – final diagnosis, disposition decision, treatment plan and follow-up plan.

Each participant's simulation session will last approximately one hour. All sessions will be scheduled during off-duty hours to ensure voluntary participation and to avoid disruption of patient care.

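### The confirmatory model has a participant random intercept only, so its 95% interval for a contrast between two sessions is not reliably calibrated

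*Combined protocol and SAP*

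**What the plan says.** Section C.11 analyses the per-vignette proportion of management actions "using a generalized linear mixed-effects model with binomial distribution and logit link". The fixed effects are arm, period, sequence, scenario type (three levels), cadre, years of experience and comfort with apps. The random part is one sentence: "Random intercepts will be specified for participant to account for repeated measures". Process quality is modelled "with the same fixed and random effects as above", and the binary outcomes use the same structure. The terms of the time model are not listed.

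Section C.11 makes the crossover analysis of the primary outcome the sole confirmatory analysis and promises an adjusted mean difference with a 95% CI. It does not state the item denominator or weight, any session, vignette or case effect, an overdispersion check, robust standard errors or a small-sample reference distribution.

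On size, section C.4 says "We anticipate enrolling approximately 16 participants" and "Each participant will complete 12 simulated scenarios, yielding an estimated 192 scenario-level observations". Sections C.6 and C.8 allot six vignettes to each condition, with the A and B case sets randomly assigned to the two periods for each participant.

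**The concern.** The arm is applied to a whole session. A participant intercept describes what is common to all 12 of a clinician's vignettes, and that part drops out when the two sessions are compared. What remains, apart from the fixed effects, is variation between sessions, between vignettes and between items. The planned model recognises only the last, as binomial sampling.

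The documents give reasons to expect the other two:

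- Blank answers in a completed scenario count as incorrect (C.11), so one empty field can fail several items together.
- In the sample key (Appendix E), the immediate treatment and the later plan both follow from recognising the same degree of dehydration.
- Cases of one scenario type differ in severity and in patient age (C.8), but no term represents the individual case.
- App benefit may differ between clinicians. With one session per arm, that difference acts as session variation.

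At stake is the calibration of the one confirmatory interval. Section C.4 also intends the effect estimates to inform the next trial's design.

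**Working it through.** **The plan's own figure.** 16 × 12 = 192 scenario-level observations, as stated. The number of sessions is 16 × 2 = 32, each with 6 vignettes.

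**Items per vignette (m).** No count is given for the primary outcome. The assessor sheet in Appendix E, common to all cases, has six fields; three concern investigations or treatment, which is how C.9 defines the outcome. The sample process-quality score in Appendix C is out of 8. I therefore use m = 3 and 6 for the primary outcome and m = 8 for process quality.

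**Approximate variance.** Write s for the participant-by-period (session) SD and v for the vignette SD, both on the logit scale, and p for the success probability. With n participants:

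Var(arm log odds ratio) ≈ (2/n) × [s² + v²/6 + 1/(6·m·p(1−p))]

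The planned model keeps only the last term. Take n = 16 and assume p = 0.5.

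- Model SE, m = 6: √(0.125 × 1/9) = √0.0139 = 0.118.
- True SD with s = 0.3, v = 0: √(0.125 × (0.09 + 0.111)) = √0.0251 = 0.159.
- 1.96 × 0.118/0.159 = 1.45, so the type I error is about 15%.
- Unweighted, one trial per vignette (m = 1 in the formula): √(0.125 × 0.667) = 0.289 whatever the real m, against a true SD of 0.118 at m = 6 with no extra variation. The interval is then too wide.

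A session SD of 0.3 corresponds to an App effect that varies between clinicians with SD 0.3 × √2 = 0.42 logit.

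**Simulation.** No App effect; participant SD 0.5; item-count weighting; 600 runs per setting; the participant-level covariates omitted. None of the SDs is in the documents. Coverage (%) of the planned 95% interval:

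| SDs: session / vignette / case | m = 3 | m = 6 | m = 8 |
|---|---|---|---|
| 0 / 0 / 0 | 94.3 | 95.5 | 94.5 |
| 0 / 0.5 / 0 | 93.8 | 92.3 | 90.7 |
| 0 / 1.0 / 0 | 92.3 | 86.8 | 83.7 |
| 0 / 1.5 / 0 | 89.7 | 81.7 | 77.3 |
| 0.3 / 0 / 0 | 90.2 | 86.5 | 83.7 |
| 0.5 / 0 / 0 | 84.8 | 74.7 | 70.7 |
| 0 / 0 / 0.7 | 91.2 | 89.5 | 87.8 |
| 0.3 / 0.7 / 0.5 | 87.8 | 80.8 | 75.3 |
| 0.5 / 1.0 / 0.5 | 81.7 | 71.3 | 65.7 |

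Monte Carlo error at 85% coverage is √(0.85 × 0.15/600) = 1.5 points. In the fifth row at m = 6 the mean SE was 0.122 and the empirical SD 0.158, close to the formula. Fitted unweighted, the SE was about 0.29 throughout and coverage 97.7 to 100%. A participant-level period-adjusted t-test covered 93.3 to 95.8% in every setting.

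**Effect of adding the missing terms** (m = 6, no case effect, 200 runs):

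| SDs: session / vignette | Planned model: SE, empirical SD, coverage | With session and vignette intercepts |
|---|---|---|
| 0.3 / 0.7 | 0.122, 0.170, 85.5% | 0.177, 0.175, 94.0% |
| 0.5 / 1.0 | 0.122, 0.211, 75.5% | 0.234, 0.228, 94.0% |

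**Unequal item difficulty** makes a checklist total less variable than a binomial and offsets part of this. Type I error of the planned model, 400 runs per setting, by assumed item-difficulty SD:

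| m; vignette SD; session SD | Equal items | SD 1.0 | SD 1.5 | SD 2.0 |
|---|---|---|---|---|
| 6; 0.5; 0.2 | 10% | 6% | 5% | 3.5% |
| 6; 0.7; 0.3 | 16% | 13% | 10% | 6% |
| 3; 0.7; 0.3 | 12.5% | 9% | 6.5% | 5% |

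A further simulation, also 400 null trials per setting under assumed SDs, gave 11 to 21% with 6 equal items and about 8% with strongly unequal items. A period-adjusted paired analysis gave 5 to 6% in the same settings.

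**The case against.** A reader might infer that the interval is bound to be too narrow. The documents do not support that. C.11 describes a 0-1 proportion and gives no denominator; fitted unweighted, the interval errs the other way. Unequal item difficulty, plausible from the sample key, can also remove the inflation when session variation is small. What stands is that neither reading is calibrated by design.

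A reader might also quote much larger error rates. With ten items per vignette, simulation gives 27 to 36%. No section supports ten items for the primary outcome, and with three items and mild extra variation the same calculation gives about 8%.

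Nor does the model treat all observations as independent. Independence is conditional on participant, and correlation common to all 12 vignettes is modelled. Item clustering does not arise for the binary outcomes, which have one response per vignette (for diagnostic accuracy, one per stage); there the gap is the session term.

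The first-exposure sensitivity analysis helps little. Each participant then has one session, so the participant intercept does carry session variation. But it compares about eight participants per arm and leaves the confirmatory interval unchanged.

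Finally, this is a feasibility-sized pilot with no stated alpha or decision rule, and C.4 passes on effect estimates without saying that the interval is passed on. That lowers the severity. It does not excuse a poorly calibrated interval in the one analysis called confirmatory.

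**Conclusion.** The point holds as a calibration fault whose size cannot be determined. The only random effect cancels from the App contrast, and nothing else in the plan covers session-level or vignette-level variation.

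With item-count weighting, 3 to 6 equally difficult items and a session SD of at most 0.3, type I error runs from near nominal to about 20% (100 − 80.8 = 19.2% in the combined setting). A session SD of 0.5 would take it to between 15.2% and 28.7%. Unequal difficulty lowers these figures. All rest on assumed variance components and item counts.

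The unstated conversion from log odds ratio to mean difference is a lesser gap: standardisation can supply it, but the plan should say so. Severity: should-fix.

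**What to change.** **Primary outcome and process quality.** Analyse the vignette proportion with a linear mixed model: random intercepts for participant and participant-by-period; fixed effects for arm, period, sequence, scenario type and A/B set (or case); Kenward-Roger degrees of freedom. This gives the promised adjusted mean difference directly and follows the paired crossover analysis in spirit. With complete data the reference is a t distribution on about 16 − 3 = 13 df with the set term, or 14 without it.

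**If the logit model is kept.** State the item denominator and that proportions are weighted by it. Add participant-by-period and vignette-level random intercepts and a set or case term, use a small-sample t reference, and obtain the mean difference by standardisation.

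**Binary and time outcomes.** Add the participant-by-period intercept and the set or case term; no vignette-level intercept is needed.

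**Fallback.** State in advance that a singular fit leads to the participant-level period-adjusted paired analysis.

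The set or case term matters because the sets are randomised to periods for each participant and need not balance across arms. Case variation alone (SD 0.7) lowered coverage to between 87.8% and 91.2%, although successful matching of the case pairs would reduce this. The calibration checks above are for the paired analysis and for the extended logit model without case effects; the linear model with a set term was not itself simulated.

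**Cost.** SAP wording and a few lines of code, with no extra data. The interval will be wider in most settings, and singular fits are possible with 16 participants.

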The Organization for the Advancement and Support of Emergency Systems (OASES) App is a CDSS developed in 2025 by the University of Milano-Bicocca. Its development was undertaken as part of a broader quality improvement collaboration between the University of Milano-Bicocca and [name] Hospital, aimed at strengthening emergency and acute care services in rural Uganda. The App is an intuitive, tablet-based system that digitalizes validated triage and emergency care algorithms derived from WHO frameworks. Designed for offline use in hospitals with limited infrastructure, it guides frontline clinicians, particularly those with limited training, through systematic triage, diagnosis, and treatment steps for common emergency presentations in real time, while simultaneously collecting structured clinical data. The current version of the App includes a triage algorithm based on the Interagency Integrated Triage Tool (IITT) and three condition-specific modules for the management of diarrhea, dyspnea, and seizures in both adults and children. To date, the OASES App has not been tested in clinical or simulated settings. Prior to implementation in rural emergency departments, it therefore requires rigorous evaluation in simulation to determine its effectiveness, usability, and feasibility among intended end-users.

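### The logistic models for triage, disposition and diagnostic accuracy have no finite odds ratio if one App cell of about 48 vignettes is error-free, and C.11 gives no fallback

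*Combined protocol and SAP*

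**What the plan says.** C.11 Statistical Analysis defines the primary model first: "The model will include fixed effects for study arm (App vs. control), period (first vs. second session), sequence (allocation order"), followed by scenario type, cadre, years of experience and comfort with mobile apps, with a random intercept per participant. Triage, disposition and diagnostic accuracy are then analysed "using mixed-effects logistic regression, with the same fixed and random effects structure as above. Results will be reported as adjusted odds ratios with 95% CIs".

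C.9 scores each of these as correct or incorrect per vignette. For triage the score is "Correct assignment to Interagency Integrated Triage Tool (IITT) category (Red/Emergency, Yellow/Urgent, Green/Non-urgent) compared with the case-specific expected category (binary"). Section A states: "The current version of the App includes a triage algorithm based on the Interagency Integrated Triage Tool (IITT").

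On size, C.4 says "We anticipate enrolling approximately 16 participants" and "Each participant will complete 12 simulated scenarios, yielding an estimated 192 scenario-level observations"; C.8 divides the twelve "with six scenarios per study arm (two diarrhea, two dyspnea, and two seizures").

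The only sensitivity analysis is in C.11: "a first-exposure parallel analysis will be conducted, in which only the first period for each participant is analyzed". C.11 names no interval method, no penalised, exact or Bayesian fit, and no rule for a cell without errors or a model that does not converge. It treats all secondary outcomes as exploratory.

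**The concern.** In a two-sequence, two-period crossover, arm is the interaction of sequence and period. Fitting arm, period and sequence together therefore uses up all the information between the four cells, and the arm coefficient depends on the logit of every cell separately. A single cell at 100% correct has an infinite logit. The arm estimate then becomes infinite even when the other App cell contains errors and the overall App accuracy is below 100%.

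The chance of this rises with App accuracy, so the planned summary is most likely to break down when the App performs best. The three outcomes are named secondary objectives in section B, and C.4 says the pilot is to supply preliminary effect estimates for the design and power calculations of a larger trial. An odds ratio with no finite value or upper limit cannot serve that purpose. A rescue method chosen after the data are seen would be an unplanned analysis.

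**Working it through.** **Inputs.** About 16 participants and 12 scenarios each (C.4); six scenarios per arm (C.8); 1:1 order in permuted blocks of 2 within two cadre strata (C.6); model terms from C.11. App accuracy p is an assumption, shown over a range, because the documents give none.

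**The plan's own figure.** 16 × 12 = 192 scenario-level observations, as C.4 states.

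**Cell size.** With an 8:8 split, each sequence-by-period cell has 8 × 6 = 48 vignettes. If both strata are odd the split can be 7:9, giving cells of 42 and 54.

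**Saturation.** Two sequences × two periods = four cells. Intercept, arm, period and sequence are four parameters, and the 4 × 4 cell design matrix has rank 4. Inverting it gives

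arm log-OR = ½ × [(sum of the two App cell logits) − (sum of the two control cell logits)].

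If one App cell has no errors and the other three cells are mixed, this is +∞. An error-free control cell, with the rest mixed, gives −∞, that is, an odds ratio of 0. The other covariates and the random intercept do not help: the parameter direction that raises only the error-free cell leaves the other three unchanged, whatever the participant's intercept.

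**Check on the full planned model.** One illustrative simulated data set had correct counts of 48/48 (App) and 23/48 (control) in one sequence, and 27/48 (control) and 39/48 (App) in the other. Profile log-likelihood by arm log-OR:

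| Arm log-OR | 2 | 3 | 4 | 6 | 8 | 15 |
|---|---|---|---|---|---|---|
| With sequence | −86.96 | −84.10 | −83.35 | −83.192 | −83.189 | −83.189 |
| Without sequence | −88.00 | −86.04 | −86.78 | −90.52 | −93.96 | −102.07 |

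With sequence the curve never turns down, so no finite estimate exists. Without sequence it peaks near 3.

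**How often.** With independent vignettes, q = p^48 is the chance that a given App cell is error-free, 1 − (1 − q)² the chance that at least one of the two is, and q² = p^96 the chance that both are. Both are needed on the App side once sequence is dropped.

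| App accuracy p | One given cell, q | At least one of two | Both |
|---|---|---|---|
| 0.85 | 0.04% | 0.1% | 0.0% |
| 0.90 | 0.6% | 1.3% | 0.0% |
| 0.95 | 8.5% | 16% | 0.7% |
| 0.97 | 23% | 41% | 5% |
| 0.98 | 38% | 61% | 14% |
| 0.99 | 62% | 85% | 38% |

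A 7:9 split changes little: 1 − (1 − 0.95^42)(1 − 0.95^54) = 17% at 0.95. If clinicians differ (random-intercept SD 1.0 on the logit scale, same average accuracy), the third column becomes 3%, 22%, 46%, 64% and 86% at 0.90 to 0.99.

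**First-exposure analysis.** With period 1 only, arm and sequence coincide and there is one App cell, so the column for one given cell applies: 9%, 23%, 38% and 62% at 0.95, 0.97, 0.98 and 0.99.

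**What a penalised fit does.** For the four cells alone, ignoring covariates and the random intercept, a Firth penalty adds ½ to the correct and incorrect counts in each cell. The cell logits become ln(48.5/0.5) = 4.575, ln(39.5/9.5) = 1.425, ln(23.5/25.5) = −0.082 and ln(27.5/21.5) = 0.246. The arm log-OR is ½ × [(4.575 + 1.425) − (−0.082 + 0.246)] = 2.92, an odds ratio of about 18.5. The period-adjusted difference in proportions for the same cells is ½ × [(48 − 23)/48 + (39 − 27)/48] = 38.5 percentage points.

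**The case against.** **The trigger is assumed.** The problem is negligible below about 90% App accuracy and matters from about 95%. The text supports near-ceiling accuracy mainly for triage, where the App runs the tool that defines the right answer. Elsewhere it points the other way: the App is untested (A), users get only a short orientation (C.7), facilitators give information only on request and participants are told the App may be wrong (Appendix C), diagnosis is free text at two stages (C.9, Appendix D), and blanks count as incorrect (C.11). This stands, and limits the point to a conditional risk.

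**A reader might infer that the plan would report a large App benefit as non-significant.** The documents do not support that. C.11 specifies no Wald test for these outcomes and calls them exploratory. In a simulation of the planned model (300 trials per setting, control accuracy 0.80, participant SD 0.7), Wald power at App accuracy 0.95, 0.97 and 0.98 was 73%, 51% and 38%, but the likelihood-ratio test on the same model had 91%, 97% and 99%. The loss of evidence is specific to Wald inference. A profile-likelihood lower limit stays finite; in the example above it lies between log-ORs of 2 and 3. What is lost under any unpenalised likelihood method is the point estimate and the upper limit.

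**The failure is visible.** A huge odds ratio or a convergence warning would alert the analyst. True, but the plan does not say what to do next.

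**Sequence has a purpose.** Section B lists learning and carryover as an objective, and the sequence contrast bears on it, although confounded. This stands, so the term should be reported separately.

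**A reader might also infer that the odds ratio should give way to a risk difference.** That would change the planned estimand, drop the planned covariates and lose participants seen in only one period. The defect does not require it.

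**Conclusion.** The gap is real but conditional. As C.11 is written, one error-free App cell leaves the planned odds ratio without a finite value or upper limit, and an error-free control cell sends it to 0. The algebra is exact. The frequency rests on about 16 participants split about evenly, all scenarios completed, roughly independent vignettes, and an App accuracy that the documents do not state: about 1% at 0.90, 16% at 0.95 and 61% at 0.98. Triage is the most plausible case; disposition and diagnosis share the model but have less textual support for a ceiling. The confirmatory analysis of the primary outcome is not affected. The change is still worth making before analysis, because these estimates are meant to feed the next trial and the remedy is nearly free.

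**What to change.** In C.11, for triage, disposition and diagnostic accuracy, including the first-exposure analysis:

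1. Fit the models by penalised likelihood (Firth-type, or a weakly informative prior on the fixed effects), with profile-likelihood or posterior intervals instead of Wald intervals.
2. Take the main App odds ratio from the model without the sequence term. Report the sequence term separately, for the carryover objective. Dropping sequence is not enough alone, since both App cells could still be error-free (14% at accuracy 0.98), so the penalty is needed as well.
3. Beside the odds ratio, not in its place, report the period-adjusted within-participant difference in proportion correct. Average the App-minus-control differences within each sequence, average the two sequence means, and give a 95% t-interval on 16 − 2 = 14 degrees of freedom. This estimate is always finite.

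Cost: a few lines of SAP text and code, no new data or participants, and slight shrinkage of the odds ratio towards 1. The supplementary difference is not covariate-adjusted and uses only participants with both periods, which should be stated where it is reported.
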